## Please refer to the Investigator Brochure Addendum for the Comprehensive Adverse Events and Potential Risks (CAEPR) List.

Adverse events reported on BMS-936558 (Nivolumab, MDX- 1106) trials, but for which there is insufficient evidence to suggest that there was a reasonable possibility that BMS- 936558 (Nivolumab, MDX-1106) caused the adverse event:

CARDIAC DISORDERS - Atrial fibrillation; Atrioventricular block complete; Heart failure; Pericarditis; Ventricular arrhythmia

EAR AND LABYRINTH DISORDERS - Vestibular disorder

ENDOCRINE DISORDERS - Endocrine disorders - Other (autoimmune thyroiditis); Endocrine disorders - Other (hypopituitarism)

EYE DISORDERS - Eye disorders - Other (iridocyclitis); Optic nerve disorder GASTROINTESTINAL DISORDERS - Constipation; Duodenal ulcer; Enterocolitis; Flatulence; Gastrointestinal disorders - Other (mouth sores); Mucositis oral; Vomiting

GENERAL DISORDERS AND ADMINISTRATION SITE CONDITIONS - Chills; Edema limbs; Malaise; Pain

HEPATOBILIARY DISORDERS - Bile duct stenosis; Hepatobiliary disorders - Other (autoimmune hepatitis) IMMUNE SYSTEM DISORDERS - Anaphylaxis; Immune system disorders - Other (limbic encephalitis)

INFECTIONS AND INFESTATIONS - Bronchial infection; Encephalitis infection; Lung infection; Sepsis; Upper respiratory infection

INVESTIGATIONS - Alkaline phosphatase increased; CPK increased; GGT increased; Investigations - Other (blood LDH increased); Investigations - Other (CRP increased); Investigations - Other (eosinophil count increased); Investigations - Other (protein total decreased); Investigations - Other (thyroxine free increased); Investigations - Other (triiodothyronine free decreased); Investigations - Other (WBC count increased); Lymphocyte count increased; Weight loss; White blood cell decreased

METABOLISM AND NUTRITION DISORDERS - Dehydration; Hyperuricemia; Hypoalbuminemia; Hypocalcemia; Hyponatremia; Hypophosphatemia

MUSCULOSKELETAL AND CONNECTIVE TISSUE DISORDERS - Arthritis; Back pain; Musculoskeletal and connective tissue disorder - Other (musculoskeletal pain); Musculoskeletal and connective tissue disorder - Other (polymyalgia rheumatica); Myalgia; Pain in extremity

NEOPLASMS BENIGN, MALIGNANT AND UNSPECIFIED (INCL CYSTS AND POLYPS) - Neoplasms benign, malignant and unspecified (incl cysts and polyps) - Other (histiocytic necrotizing lymphadenitis)

NERVOUS SYSTEM DISORDERS - Dizziness; Headache; Intracranial hemorrhage; Nervous system disorders - Other (autoimmune neuropathy); Stroke

#### PSYCHIATRIC DISORDERS - Insomnia

RENAL AND URINARY DISORDERS - Hematuria; Renal and urinary disorders - Other (nephritis); Renal and urinary disorders - Other (tubulointerstitial nephritis)

RESPIRATORY, THORACIC AND MEDIASTINAL DISORDERS - Bronchospasm; Cough; Dyspnea; Hypoxia; Respiratory failure; Respiratory, thoracic and mediastinal disorders - Other (interstitial lung disease); Respiratory, thoracic and mediastinal disorders - Other (lung infiltration); Wheezing

SKIN AND SUBCUTANEOUS TISSUE DISORDERS - Alopecia; Dry skin; Hyperhidrosis; Pain of skin; Periorbital edema; Photosensitivity; Rash acneiform; Skin and subcutaneous tissue disorders - Other (rosacea); Toxic epidermal necrolysis

VASCULAR DISORDERS - Flushing; Hypertension; Hypotension; Vasculitis Note: BMS-936558 (Nivolumab, MDX-1106) in combination with other agents could cause an exacerbation of any adverse event currently known to be caused by the other agent, or the combination may result in events never previously associated with either agent. Adverse events occurring in < 1%, post marketing, and/or case reports: Hemophagocyticlymphohistiocytosis, rhabdomyolysis and polymyositis have been reported in patients received more than one dose of combination therapy (nivolumab 3 mg/kg and ipilimumab 1 mg/kg every 3 weeks) for the treatment of metastatic gastric adenocarcinoma and advanced bladder cancer, respectively.

2. Pregnancy and Lactation: Pregnancy: Adverse events were observed in animal reproduction studies. Nivolumab may be expected to cross the placenta; effects to the fetus may be greater in the second and third trimesters. Based on its mechanism of action, nivolumab is expected to cause fetal harm if used during pregnancy. Women of reproductive potential should use highly-effective contraception during therapy and for at least 6 months after treatment has been discontinued. Men receiving nivolumab and who are sexually active with women of child bearing potential should adhere to contraception for a period of 7 months after the last dose of nivolumab.

Lactation: It is not known if nivolumab is excreted into breast milk. Due to the potential for serious adverse reactions in the nursing infant, the manufacturer recommends women to discontinue breastfeeding during treatment with nivolumab.

3. Drug Interactions: Nivolumab is not expected to have any effect on cytochrome P450 or other drug metabolizing enzymes in terms of inhibition or induction, and is, therefore, not expected to induce these types of PK-based drug interactions. No incompatibilities between nivolumab injection and polyvinyl chloride (PVC), non-PVC/non-DEHP (di(2-ethylhexyl)phthalate) IV components, or glass bottles have been observed.

We will study the BTC tumor microenvironment through the use of pre-treatment tissue collection (at all sites) as well as on-treatment (for patients at University of Michigan) and post-treatment (optional for patients enrolled at all sites) tumor biopsies. Identification of important biologic subsets of BTC patients that may have clinical efficacy from nivolumab and rucaparib will be the overarching goal of this translational science. Tumor from core biopsies will be examined histologically by immunohistochemistry (IHC), immunofluorescence (IF), and RNA analysis. Posttreatment biopsy tissue will be separated into sections for paraffin embedding, fresh frozen in OTC, and fresh frozen in RNAlater. Whole genomic DNA will be evaluated for mutational analysis). Biologic readouts for PD-1 and CTLA4 response biomarkers will be assessed along with specific markers of tumor infiltrating leukocytes (TILs). TILs and their subsets will be assessed using markers by IHC (e.g. CD4, CD8, FoxP3 (Treg), CD14 or CD68 (TAMs), CD11c (DCs)). Response biomarkers will be determined by IHC or IF (e.g. B7-H1 (PD-1L), CD80, CD86, B7-H4, B7-HDC (PD-L2), CTLA4, CD28, LAG3, Tim-3, CD40, OX40)46,47. Cytokine signaling representative of Th1. Th2, and other immune pathway signature gene expression will be determined by transcriptomic assessment (RNAseq) and analyzed using Gene Set Enrichment Analysis software (GSEA) at the University of Michigan. Furthermore, we will study peripheral blood for the presence of peripheral blood mononuclear cell subsets following Ficoll separation and multiplex FACS analysis for T cell subset markers and co-stimulatory/inhibitory markers Biologic markers and RNA expression will be examined in the context of patient efficacy.

#### 10.1 Tissue Collection Guidelines (See Laboratory Manual for details)

#### Pre- and Post-treatment (for patient at all sites excluding University of Michigan):

#### 1. Pre-treatment: Screening:

Formalin-fixed paraffin-embedded (FFPE) diagnostic tumor tissue block(s) is preferred to allow IHC and genomic/immune profiling. If not, then up to 20 FFPE 5 micron slides plus a H&E slide from a core biopsy block will be required for IHC. Procurement of tissue is mandatory to complete correlative studies.

#### 2. Post-treatment:

Tissue should be collected, processed and shipped to University of Michigan as detailed in the lab manual.

#### Pre-, On- and Post-treatment (for patients enrolled at University of Michigan):

- 1. Pre-treatment: Screening
- 2. On-treatment: Cycle 4 Day 1
- 3. Post-treatment: EOT

Please refer to the lab manual for details.

A CLIA certified targeted gene panel will be run on the post-treatment tissue *without* additional cost to the patient and the report will be released to the treating investigator to inform future therapy.

#### 10.2 Blood Collection Guidelines

Blood samples will be collected at three different time-points for each patient as detailed below:

- 1. Pre-treatment: Cycle 1 Day 1 2. On-treatment: Cycle 3 Day 1
- 3. Post-treatment: EOT

Blood will be collected, processed and shipped to the University of Michigan as detailed in the lab manual.

#### 10.3 Specimen Banking

Patient samples collected for this study will be retained at University of Michigan. Specimens will be stored indefinitely or until they are used up. If future use is denied or withdrawn by the patient, best efforts will be made to stop any additional studies and to destroy the specimens.

All CT scans should be de-identified using trial patient and site IDs and shipped to the University of Michigan for banking and exploratory endpoint assessment.

Specimens being stored long-term for potential use not outlined in the protocol are subject to University Policy Governing Tissue Sample Collection, Ownership, Usage, and Disposition within all UMMS Research Repositories.

#### 11.0 STATISTICAL CONSIDERATIONS

#### 11.1 Study Design/Study Endpoints

This protocol will enroll patients with advanced unresectable BTC who have received at least 4 months of platinum-based front-line systemic chemotherapy with last dose within 4 weeks of informed consent. The primary endpoint is PFS rate at 4 months following the initiation of study treatment. Secondary endpoints include the calculation of the ORR, median PFS and OS (from start of study treatment and 1st line platinum-based therapy), and the incidence of adverse events.

#### 11.2 Sample Size and Accrual

The investigators hope to enroll patients after 4-6 months of first line platinum therapy without progression. The sample size of this trial is based on the hypothesis that we will improve upon the expected proportion of patients surviving without progression after 4 months of investigational therapy. We will accrue 32 evaluable patients to this trial. Evaluable patients are compliant with study treatment and observed for progression-free survival events, progression (requiring study discontinuation), death, or lack of events at 4 months. Patients non-complaint with study treatment or lost to follow-up (either not secondary to toxicity) will be replaced. Based on the ABC-02 trial, PFS was estimated at 72% and 60% after 4 and 6 months of first line gemcitabine and cisplatin, similar to the initiation point of our study. PFS was 51% and 32% at 8 and 10 months, similar to the end of the treatment period for the primary outcome assessment in this trial. Using a conditional probability argument, combined with the assumption that patient accrual to this study will follow an approximate uniform distribution over the 4 to 6 months of primary therapy for the patients accrued, we can accept the average of the PFS estimates for each period (4-6 months (66%) and 8-10 months (41.5%)) to correspond to our trial time period. We can then standardize the ABC-02 PFS data so that the 4-6 month estimate is 100% to correspond to the start point for patients in this trial and the estimate for 4 months thereafter, 63% (0.415/0.66). For our trial, we hope to improve the PFS rate from 63% for these patients to 85%. With our proposed sample size of 32 patients this trial will have 80% power to detect this difference significantly, with 5% type 1 error, using a 1sided test

#### 11.3 Study Populations

The evaluable population for the primary, secondary, and safety endpoints is the intent-to-treat (IIT) population as defined in section 5.10.

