# 5.10 Patient Replacement

All patients that receive at least one dose of study therapy will be considered evaluable for toxicity and will be considered a member of the intent-to-treat (IIT) population.

Patients enrolled on the study will be replaced and not considered a member of the IIT for the following reasons

- 1. Patients who did not receive even one dose of investigational therapy on study.
- 2. Patients that withdraw consent for study therapy prior to first response evaluation not secondary to toxicity.
- 3. Patients meeting off study criteria 5.9.1 and/or 5.9.3 not secondary to toxicity.
- 4. Patients meeting off study criteria 5.9.2 and/or 5.9.5

We expect the proportion of patients needed to be replaced to be extremely small for this clinical trial, at or less than 10% of those enrolled. Maximum enrollment to this trial will be increased to 35 patients if the necessity to replace patients is encountered.

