# 7.2 Safety/Tolerability

Analyses will be performed for all patients having received at least one dose of study drug. The study will use the CTCAE version 5.0 for reporting of non-hematologic adverse events (http://ctep.cancer.gov/reporting/ctc.html).

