#### 11.4 Data Analyses Plans

The primary endpoint is the progression-free survival proportion measured after 4 months of study treatment for patients in the IIT population. This endpoint is defined as the proportion of evaluable patients alive and progression-free after 4 months of study treatment in the event of no loss to follow-up and/or early patient discontinuation. The outcome is expected to be observed for each patient. In the event that either loss to follow-up or early discontinuation occurs (either not secondary to toxicity), the 4-month PFS will be estimated using the product-limit method of Kaplan and Meier. Follow-up time will be defined as time from the date of first study treatment (PFS1) and 1st line platinum-based therapy (PFS2) until the date of radiological (as per combined RECIST v1.1 and irRECIST criteria) or clinical progression (leading to withdrawal from the study treatment), or loss to follow-up due to toxicity or non-compliance with study procedures, or death from any cause, whichever comes first. Follow-up time will be censored at the date of last disease evaluation. Estimates for the median and 75th percentiles with 95% confidence intervals will be reported. In order to adjust for the patient's exposure to primary platinum-based therapy, a secondary analysis will utilize the Cox proportional hazards model with exposure time entered as an adjustment covariate as either a continuous covariate or as 4 months of exposure versus more than 4 months of exposure. OS will be similarly estimated and summarized with follow-up time calculated from the date of first study treatment (OS1) and 1st line platinum-based therapy (OS2) until date of death or censoring. ORR will be determined as per the irRECIST guidelines for the IIT population. Other safety data (e.g., laboratory safety parameters, vital signs, and new physical examination findings) will be summarized descriptively for the IIT population by reporting counts and percentages, with exact binomial confidence intervals where appropriate. Adverse events will be reported per the NCI Common Toxicity Criteria for Adverse Events (CTCAE) version 5.0.

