#### 11.5 Early Stopping Rules Due to Toxicity

In order to protect patients from potential undue severe toxicity of this regimen, we have implemented stopping rules for documented SAE events that are at least possibly attributable to the study regimen. Using data from study of rucaparib monotherapy as maintenance therapy in ovarian cancer (phase 3 ARIEL3 trial; Coleman RL et al. Lancet. 2017 Oct 28;390(10106):1949-1961) as a guide, which had a SAE rate of 21% - defined as the percentage of patients experiencing at least one SAE during study treatment. In addition, the investigation of nivolumab in hepatocellular carcinoma (CHECKMATE-040 trial; El-Khoueiry AB et al. Lancet. 2017 Jun 24;389(10088):2492-2502) had a SAE rate of 4%. During the conduct of this proposed study, if we become confident from accumulating study data that the SAE rate, defined in the same way, involves more than 30% patients, then we will halt accrual on the trial in order to convene the data safety monitoring board (DSMB). The DSMB will review types and outcome of toxicity events and to recommend study closure or changes that could improve the trial.

To operationalize this stopping rule we have used a Bayesian sequential stopping rule under the beta-binomial relationship between prior expectation of toxicity and accumulating toxicity data. We have used a pessimistic and slightly informative prior, the uniform, to suggest that prior to study data we believe the percentage of SAE is equally like between 0 and 100%, with an average of 50%. If the posterior probability after study data is 80% or greater that the SAE probability per patient is 30% or greater, we will halt the trial. The following table lists the number of patients accrued and the number of patients experiencing an SAE to trigger stopping the trial. The rule is implemented after 5 patients are accrued.

| Number of patients on study treatment | Number experiencing SAE |
|---------------------------------------|-------------------------|
| 1 – 5                                 | No rule to apply –      |

|         | too early |
|---------|-----------|
| 6 – 10  | 6         |
| 11 – 12 | 7         |
| 13 – 14 | 8         |
| 15 – 16 | 9         |
| 17 – 18 | 10        |
| 19 – 20 | 11        |
| 20 – 22 | 12        |
| 23 – 24 | 13        |
| 25 – 26 | 14        |
| 27 – 28 | 15        |
| 29 – 30 | 16        |
| 31 – 32 | 17        |

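### Section 11.3 ties the safety population to a set from which section 5.10 removes some dosed patients, contradicting 5.2, 7.1.1, 7.2 and 5.10's own first sentence

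*Combined protocol and SAP*

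**What the plan says.** Four parts of the combined protocol and SAP bear on who is counted for safety.

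- **11.3 Study Populations** uses one set for everything: "The evaluable population for the primary, secondary, and safety endpoints is the intent-to-treat (IIT) population as defined in section 5.10".
- **11.4 Data Analyses Plans** says of laboratory values, vital signs and examination findings that they "will be summarized descriptively for the IIT population by reporting counts and percentages, with exact binomial confidence intervals where appropriate". Its next sentence, on adverse events, gives the grading system and names no population, so for adverse events 11.3 is the governing text.
- **5.10 Patient Replacement** opens inclusively: "All patients that receive at least one dose of study therapy will be considered evaluable for toxicity", and places those patients in the intent-to-treat set. It continues: "Patients enrolled on the study will be replaced and not considered a member of the IIT for the following reasons". The reasons are:
  1. "Patients who did not receive even one dose of investigational therapy on study";
  2. withdrawal of consent for therapy before the first response evaluation, unless due to toxicity;
  3. off-study criteria 5.9.1 (consent withdrawn) or 5.9.3 (unable to comply), unless due to toxicity, with no time limit;
  4. off-study criteria 5.9.2 (loss of free consent) or 5.9.5 (pregnancy), with no toxicity exception.
- **7.2 Safety/Tolerability** says: "Analyses will be performed for all patients having received at least one dose of study drug". Sections 5.2 and 7.1.1 likewise make every treated patient evaluable for toxicity.

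Section 5.10 allows enrolment to rise from 32 to 35 if replacements are needed, and expects replacements to be no more than 10% of those enrolled.

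**The concern.** An analyst building the safety tables cannot satisfy both 11.3 and 7.2. Under 11.3, read with the list in 5.10, a patient who received study drug and then left for one of the listed reasons is outside the safety denominator, and that patient's recorded events are outside the numerator. Under 7.2 the same patient is in.

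The toxicity qualifier in reasons 2 and 3 concerns why the patient left, not what happened while on treatment. Reason 3 has no time limit. A patient treated for months with recorded serious events who later withdraws for a personal reason would therefore drop out of the tables with those events. Whether that happens depends on an attribution made after dosing, in an open-label single-arm trial.

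Safety is a stated secondary objective (2.2.2), and section 5.1 describes the safety profiles of the two agents as having been evaluated individually. The safety summaries of the combination should therefore rest on an unambiguous set of everyone exposed.

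**Working it through.** **Step 1: who is removed.** Let D be the patients with at least one dose. Reason 1 in 5.10 removes every enrolled patient outside D. Anyone further removed by reasons 2 to 4 must then be in D. So:

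- set used by 11.3 = D minus the dosed patients meeting reason 2, 3 or 4;
- set used by 5.2, 7.1.1, 7.2 and the first sentence of 5.10 = D.

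The two agree only if no dosed patient meets reasons 2 to 4.

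**Step 2: how many.** Inputs: 32 evaluable patients (11.2) and a ceiling of 35 enrolled (5.10).

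- Maximum replaced = 35 − 32 = 3.
- Share = 3/35 = 8.6%, which agrees with the plan's own expectation of 10% or less.
- This is an upper bound. Patients never dosed (reason 1) use the same three places and are not missing from any safety set.

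**Step 3: effect on a reported rate.** Let k be the number of patients with a serious adverse event among the 32, and m (0 to 3) the number among the three restored patients. The reported rate is k/32 and the all-dosed rate is (k + m)/35. Both k and m are assumptions, because the documents cannot give them. Exact (Clopper-Pearson) 95% intervals are in brackets.

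| Reported on 32 | All dosed, m = 0 | All dosed, m = 3 |
|---|---|---|
| 7/32 = 21.9% (9.3 to 40.0) | 7/35 = 20.0% (8.4 to 36.9) | 10/35 = 28.6% (14.6 to 46.3) |
| 10/32 = 31.2% (16.1 to 50.0) | 10/35 = 28.6% (14.6 to 46.3) | 13/35 = 37.1% (21.5 to 55.1) |

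Restoring the patients moves the rate down by about 2 points (21.9 to 20.0) or 3 points (31.2 to 28.6) at one end. At the other it moves up by about 7 points (21.9 to 28.6) or 6 points (31.2 to 37.1). The rate rises only when m/3 exceeds k/32. With k = 7, a single event among the three is enough (8/35 = 22.9%).

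**Step 4: what does not depend on the set.** Adverse event collection to 100 days (8.1), pregnancy reporting and follow-up (8.2.5) and serious event reporting (8.4) apply to treated patients whether or not they are later replaced. The table in 11.5 is indexed by "Number of patients on study treatment", not by the intent-to-treat set.

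**Step 5: the end of the 11.5 table.** The printed rows stop at 31–32, although 35 patients could be dosed. The rule stated in the text can still be evaluated beyond 32. With a uniform prior, the posterior after s affected patients of n is Beta(1 + s, 1 + n − s), and the criterion is P(rate > 0.30) ≥ 0.80. The smallest s meeting it is 12 at n = 33 (probability 0.807), 13 at n = 34 (0.865) and 13 at n = 35 (0.837). The same criterion gives 12 at n = 31 and n = 32, where the printed table shows 17. The table and the stated rule therefore need reconciling before either is extended.

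**The case against.** The strongest reply is that 5.10 begins by making every dosed patient evaluable for toxicity and a member of the set, and that 5.2, 7.1.1 and 7.2 agree. On that view the plan as a whole leans towards including everyone dosed, and the list in 5.10 is about replacement for efficacy. This stands as evidence of intent. It does not remove the defect: the list expressly withdraws membership, and 11.3 adopts the 5.10 definition for safety without qualification.

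Three further inferences are tempting, and the documents do not support them.

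- **That toxicity rates are biased downward.** Reasons 2 and 3 keep withdrawals recognised as due to toxicity in the set, and reason 4 is not about tolerance. Step 3 shows movement in either direction. A comparison such as 9/35 (25.7%) against 6/32 (18.8%) is correct arithmetic, but it needs all three replaced patients to have been dosed and all three to have had a serious event. Setting it against the 30% figure in 11.5 is also misplaced, because that rule counts patients on study treatment, and only serious events at least possibly attributable to the regimen.
- **That treated or pregnant patients are lost to safety surveillance.** Collection, expedited reporting and quarterly committee review (section 13) continue for them. Only the analysis tables are affected.
- **That dosed patients 33 to 35 have no halting trigger.** They have no tabulated trigger. The stated posterior criterion can be computed at any number of patients.

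**Conclusion.** The point holds as a contradiction about the safety denominator. Followed as written, 11.3 and the 5.10 list produce a safety set that omits some dosed patients, against 7.2 and three other statements in the same document. The size is bounded at 3 of 35 patients (8.6%), assuming every replaced patient had been dosed and enrolment reached its ceiling. In the illustrations a reported serious event rate would change by between about 3 points down and 7 points up once those patients are restored. The direction cannot be known in advance. The 32-patient efficacy sample size, event reporting and the 11.5 count are not affected. The change should be made because the contradiction is plain and the correction costs almost nothing, not because a large distortion has been shown.

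**What to change.** - **11.3 and 11.4:** define a separate safety population of every patient who received at least one dose of either study drug, including patients later replaced. Use it for all adverse event, serious adverse event and laboratory summaries, and name it in the adverse event sentence of 11.4, which at present names no population.
- **5.10:** state that the replacement list governs the efficacy-evaluable set only and does not affect safety analyses.
- **11.5 (minor consistency point):** state that the count includes all dosed patients, replaced or not, and extend the printed table to 35, using whichever criterion is kept once the table and the stated posterior rule are reconciled.

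The cost is a sentence each in 11.3, 11.4 and 5.10, plus one sentence and a few table rows in 11.5. No new data are needed, because 5.2 and 8.1 already require toxicity assessment and event collection in these patients.
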